Since this is single-center study, there is no external site monitoring mechanism. At least 10% of individual case report forms and source documents will be reviewed to confirm that all recorded data is verifiable, accurate and complete. Areas to be assessed include informed consents and process, subject eligibility, case report form and/or source document completion/accuracy, adverse event reporting, drug accountability and the primary efficacy outcome. Data and patient outcomes will be subject to DSMB reviews.

Risk Assessment

Risks of Active Study Drug

The most common (>4% of subjects and >3% above placebo) adverse events reported for inhaled Treprostinil (TYVASO) include cough (54%), headache (41%), throat irritation / pharyngeal pain (25%), nausea (19%), flushing (15%) and syncope (6%). Quantitatively similar adverse events were reported in an open label study in 206 subjects over a mean of 2.3 years. Systemic hemodynamic effects of inhaled Treprostinil are generally minimal. A single inhaled administration of 120µg did result in arterial desaturation. The maximum dose for this study is

Version: 02-09-2018

set at 72 μ g (12 breaths). O₂ saturation will be monitored by pulse oximetry at each escalation of the dose.

Additional adverse events related to treprostinil inhalation in the respiratory tract include epistaxis, hemoptysis and wheezing. One episode of hemoptysis in the open label trial was fatal, and several cases of pneumonia (n=15) were observed. Treprostinil inhibits platelet aggregation, so an increased risk of bleeding may occur in subjects receiving anticoagulants. Similarly concomitant administration of diuretics, antihypertensive agents or vasodilators may increase the risk of symptomatic hypotension.

A retrospective cohort study was conducted from 2004-2006 (Kallen 2008) of patients who received IV formulations of either treprostinil or epoprostenol with documented bloodstream infections (BSI). Adjusted hazard ratios for all BSIs and BSIs due to gram-negative organisms, was higher for treprostinil. There are no reports of BSI following inhaled Treprostinil.

Risks of Blood Draws

All patients will have blood drawn for research purposes. Most blood will be drawn through indwelling catheters if available. Risks of drawing blood percutaneously are uncommon and include bleeding and bruising.

Minimization of Risks

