The present research will involve subjects who might be vulnerable to coercion or undue influence. As required in 45 CFR 46.111(b), we recommend that additional safeguards be included to protect the rights and welfare of these subjects. Such safeguards might include, but are not limited to: a) assessment of the potential subject's capacity to provide informed consent, b) requirement for subject's assent, c) the availability of the LAR to monitor the subject's subsequent participation and withdrawal from the study, and d) augmented consent processes. The specific nature of the additional safeguards will be left to the discretion of the IRB.

Confidentiality

Federal regulations at 45 CFR 46.111 (a) (7) requires that when appropriate, there are adequate provisions to protect the privacy of subjects and to maintain the confidentiality of data. To

maintain confidentiality, all laboratory specimens, evaluation forms, and reports will be identified only by a coded number. The coded number will be generated at random by a computer, and only the study investigators will have access to the codes. All records will be kept in a locked, password protected computer. All computer entry and networking programs will be done with coded numbers only. All paper case report forms will be maintained in a locked cabinet inside a locked office. Clinical information will not be released without the written permission of the patient, except as necessary for monitoring by the DSMB.

Adverse Event Reporting

Investigators will determine daily if any clinical adverse experiences occur during the period from enrollment through study day 28 or hospital discharge, whichever occurs first. The investigator will evaluate any changes in laboratory values and physical signs and will determine if the change is clinically important and different from what is expected in the course of treatment of patients with ARDS/ALI. If clinically important and unexpected adverse experiences occur, they will be recorded on the adverse event case report form.

For this trial, a reportable adverse event is defined as:

- 1. Any clinically important untoward medical occurrence in a patient receiving study drug or undergoing study procedures which is different from what is expected in the clinical course of a patient with ARDS/ALI, or,

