- 2. Any clinically important, untoward medical occurrence that is thought to be associated with the study drug or procedures, regardless of the "expectedness" of the event for the course of a patient with ARDS/ALI.
- 3. The following will be reported as adverse events:
 - Systemic hypotension occurring immediately after and clearly a result of the study drug.
 - Worsening of oxygenation immediately after administration of study drug.
 - Cardiac arrhythmia occurring immediately after administration of study drug.

Expected events for ARDS/ALI are untoward clinical occurrences that are perceived by the investigator to occur with reasonable frequency in the day to day care of patients with ARDS treated in an intensive care unit. Examples of adverse events that are expected in the course of ARDS include transient hypoxemia, agitation, delirium, nosocomial infections, skin breakdown, and gastrointestinal bleeding. Such events, which are often the focus of prevention efforts as part of usual ICU care, will not be considered reportable adverse events unless the event is considered by the investigator to be associated with the study drug or procedures, or unexpectedly severe or frequent for an individual patient with ALI. Examples of unexpectedly

frequent adverse events would be repeated episodes of unexplained hypoxemia. This would be in contrast to an isolated episode of transient hypoxemia (e.g. $SpO_2 \sim 85\%$), related to positioning or movement.

Investigators will report all events to United Therapeutics that are **serious** AND **unexpected** AND **study-related** within 24 hours of becoming aware of the event. The local Institutional Review Board must also be notified in a timely manner. The investigator will then submit a detailed written report to the sponsor, the DSMB, and the Institutional Review Board no later than 5 calendar days after the investigator discovers the event. A written report will be sent to the DSMB within 15 calendar days, and this also passed on to the Institutional Review Board. The DSMB will also review all adverse events during scheduled interim analyses. The written summary of the DSMB's periodic review of adverse events will be submitted to the Institutional Review Board in accordance with standards.

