Patients with ARDS have a high risk of 28-day mortality, which is approximately 45% in general ICU populations. This is because ARDS tends to be part of a syndrome of multi-organ failure that accompanies underlying severe conditions such as septic shock, severe pancreatitis, and multilobar pneumonia in patients with multiple underlying comorbidities. For that reason, 28-day mortality is the most common clinical outcome for large trials of ARDS, and in those large trials, stopping rules for safety or futility are built around 28-day mortality.

This study is a small pilot study of feasibility and safety enrolling patients with early ARDS not yet requiring mechanical ventilation. Due to its small size, a *statistical* stopping rule based on mortality or even Grade IV Adverse events is not possible. This has been confirmed by additional review by the study's statistician. Therefore a *clinical* stopping rule based on Grade 4 events or complete respiratory failure requiring intubation and mechanical ventilation, (an event that is intermediate to possible mortality in ARDS) has served as the stopping rule for this study to date.

The principle conditions for suspension of study enrollment and review of safety by the DSMB will be:

After enrollment of the first 30 patients:

- An imbalance of greater than 4 to 1 (given 2:1 randomization scheme) of any Grade 4 Adverse event from the NIH Common Terminology Criteria for Adverse Events (CTCAE)
- An imbalance of greater than 4 to 1 (given 2:1 randomization scheme) in the number of patients requiring intubation and mechanical ventilation in favor of intervention.
- A 28-day mortality rate of greater than 60% in either study arm, reflecting a rate measurably higher than expected in ARDS.

Of note: To reduce potential bias, the relationship of any Grade 4 or 5 events to study drug will be adjudicated by an expert in pulmonary hypertension and critical care, [name], who is not participating in the study and will be blinded for the assessments.

Version: 02-09-2018

Version: 02-09-2018

References:

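### Gastrointestinal bleeds and nosocomial infections judged usual for ARDS stay off the adverse event form unless attributed to treatment or unusually severe or frequent, so their rates by arm will be understated

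*Combined protocol and SAP*

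**What the plan says.** All references are to the combined protocol and SAP.

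- **What is recorded** (Adverse Event Reporting). Investigators look for adverse experiences daily, to day 28 or discharge. Then: "If clinically important and unexpected adverse experiences occur, they will be recorded on the adverse event case report form". This governs entry on the form, not only onward reporting.
- **What is expected** (same section). Events "perceived by the investigator to occur with reasonable frequency in the day to day care of patients with ARDS" in intensive care. The list reads: "Examples of adverse events that are expected in the course of ARDS include transient hypoxemia, agitation, delirium, nosocomial infections, skin breakdown, and gastrointestinal bleeding".
- **The filter** (same section). Expected events "will not be considered reportable adverse events unless the event is considered by the investigator to be associated with the study drug or procedures". The same sentence also lets through an event whose severity or frequency is beyond what is expected in that patient. There are thus two exits, attribution and unexpected severity or frequency, and both rest on the investigator's judgement.
- **Always reported** (same section, item 3). Three events just after a dose are listed: hypotension clearly due to the drug, arrhythmia, and "Worsening of oxygenation immediately after administration of study drug". The last carries no causality condition.
- **Drug risks** (Risks of Active Study Drug). "Treprostinil inhibits platelet aggregation, so an increased risk of bleeding may occur in subjects receiving anticoagulants". The section also reports 15 pneumonia cases and one fatal hemoptysis from open-label use.
- **How the counts are used.** The Safety part of the statistical section assesses safety by percentages of patients and numbers of recorded events. The DSMB section lists the same categories for the drug and placebo groups. Study Stopping Rules includes this trigger: "An imbalance of greater than 4 to 1 (given 2:1 randomization scheme) of any Grade 4 Adverse event". It also has a blinded expert outside the study adjudicate the relationship of Grade 4 and 5 events to study drug.

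**The concern.** A placebo arm lets harms that are common in the disease be compared between randomized groups without asking what caused each one. Filtering on expectedness and attribution before the event reaches the form replaces part of that comparison with a judgement about a single patient. A gastrointestinal bleed or hospital-acquired pneumonia of ordinary severity is just the kind of event an investigator would put down to the illness, and both overlap with risks the protocol names for this drug.

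Three features make this matter more here:

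- Safety is the first hypothesis, and the sample size section says that the study centers on safety and feasibility.
- Expectedness is set by the standard of ARDS care in the ICU. Enrolled patients are not yet ventilated (Exclusion Criteria, item 14; Study Stopping Rules) and may be on a floor bed (Screening). Events that are usual in an ICU may be unusual for them, so the filter may be too wide.
- The blinded adjudicator can assess only events that were recorded, so the investigator's judgement comes first.

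**Working it through.** The plan gives no figure to reproduce on this point. The first step is textual; the others show size under assumed rates.

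**1. Following events through the rules**

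| Event | Listed as expected? | Route onto the AE form | Counted elsewhere? |
|---|---|---|---|
| Gastrointestinal bleed, ordinary severity and frequency | Yes | Attribution only | No |
| Nosocomial infection, ordinary severity and frequency | Yes | Attribution only | No event count; chest radiograph score and concomitant medications are indirect |
| Epistaxis, hemoptysis | Not named | If clinically important and unexpected, or attributed | No |
| Worsening oxygenation just after a dose | Always reported | Item 3 | Yes: dose-intolerance and ventilation counts, daily SpO2/FiO2 |
| Grade 4 event judged usual for ARDS | By judgement | Attribution, or judged unexpectedly severe or frequent | Intubation and death only |

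Unexpected severity is not a CTCAE grade, and no section says that expected serious or Grade 4 events are recorded regardless.

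**2. Effect on rates and risk differences**

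Inputs: 30 patients randomized 2:1 (Study Design), so about 20 active and 10 placebo. The true event rates p1 and p0 and the recorded fraction c are assumptions; the documents give none. With the same c in both arms:

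- expected recorded counts = 20 × p1 × c and 10 × p0 × c
- expected recorded risk difference = c × (p1 − p0)

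| True rates, active v placebo | c | Expected counts | Risk difference, points |
|---|---|---|---|
| 30% v 15% | 1.00 | 6 v 1.5 | 15 |
| 30% v 15% | 0.30 | 1.8 v 0.45 | 4.5 |
| 20% v 10% | 1.00 | 4 v 1 | 10 |
| 20% v 10% | 0.50 | 2 v 0.5 | 5 |
| 20% v 10% | 0.25 | 1 v 0.25 | 2.5 |
| 30% v 10% | 1.00 | 6 v 1 | 20 |
| 30% v 10% | 0.50 | 3 v 0.5 | 10 |
| 30% v 10% | 0.25 | 1.5 v 0.25 | 5 |

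**3. Effect on the ratio between arms**

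Under equal capture the ratio of expected counts does not move: 6/1.5 = 4 and 1.8/0.45 = 4. The probability that the active count exceeds four times the placebo count (independent binomials, 20 and 10 patients) at c = 1.00, 0.50 and 0.25 is:

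- 20% v 10%: 0.49, 0.54, 0.50
- 30% v 10%: 0.67, 0.63, 0.62

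It drops clearly only at very low capture: at c = 0.10 it is 0.30 and 0.41.

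If capture differs by arm, the ratio does move. At 30% v 15% with c = 0.50 active and 0.25 placebo, the recorded rates are 0.30 × 0.50 = 15% and 0.15 × 0.25 = 3.75%. Their ratio is 4 instead of 2, and the difference is 11.25 points.

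**4. What zero recorded events would show**

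With full capture, 0 of 20 gives a one-sided 95% upper limit of 1 − 0.05^(1/20) = 13.9%. If a fraction c is recorded, the limit on the true rate is 13.9%/c: about 28% at c = 0.50, 46% at c = 0.30 and 56% at c = 0.25. In practice c is unknown.

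**The case against.** The other side has several good points, and most of them narrow the concern.

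- **The filter has a second exit.** A reader might infer that an expected event is recorded only if the drug is blamed. Unexpected severity or frequency also suffices, without attribution. This stands, and leaves only events of ordinary severity and frequency.
- **Hypoxemia is largely captured.** Because transient hypoxemia is on the list, a reader might infer that desaturation is lost. Worsening just after a dose is always reported, dose intolerance and ventilation for hypoxemia are tabulated, and SpO2/FiO2 is scheduled daily through the dosing period. Mainly isolated episodes away from dosing drop out.
- **The overlap with drug risks is limited.** Only gastrointestinal bleeding is listed as expected; epistaxis and hemoptysis are not. The bleeding statement concerns patients on anticoagulants, the 15 pneumonias are open-label cases, and the protocol knows of no bloodstream infection with the inhaled form. This limits the size of the problem but does not remove it.
- **The stopping rule is not starved.** A reader might infer that lost events disable the 4-to-1 trigger. Step 3 does not support that for capture of 25% or more, and the intubation and mortality triggers do not depend on the AE form.
- **Grade 4 events.** A reader might infer that none are collected. Those that are unexpected, attributed or unexpectedly severe are collected, and the adjudication clause suggests that the sponsor means to see them all. What remains is an ambiguity: no sentence secures it.
- **Blinding.** It limits differential filtering, although cough, reported in 54% of patients on the drug, could partly unblind. The direction of any bias in the ratio is therefore not established.

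None of this reaches the core: the recording sentence itself excludes expected events, and nothing else in the plan counts bleeding or infection.

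**Conclusion.** The concern holds for gastrointestinal bleeding and nosocomial infection, including pneumonia, of ordinary severity and frequency. Followed as written, the plan will understate their absolute rates and shrink the risk difference in proportion to the fraction recorded: from 15 to 4.5 points at assumed rates of 30% v 15% with 30% recorded. The direction of the effect on absolute rates follows from the text. The size rests wholly on assumed rates and on equal capture in the two arms, under which the expected ratio is unchanged.

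Separately, the recording rule does not guarantee that every Grade 4 event reaches the count and the adjudication that Study Stopping Rules relies on.

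A reader might also infer that a zero count would say nothing about the true rate. That goes too far: at 30% capture it would still bound the rate at about 46%, against 13.9% with full capture. It is a weak bound, and one that cannot be computed when the fraction is unknown.

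This should be changed, because safety is a main purpose of the trial and the remedy is cheap.

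**What to change.** In Adverse Event Reporting, separate recording from expedited reporting:

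1. Record on the AE form, in both arms and regardless of expectedness or attribution, every CTCAE Grade 3-5 event, every bleeding event, and every new infection or pneumonia.
2. Define a new infection as one not present at randomization. The baseline site of infection is already collected, and Appendix 1 already gives criteria.
3. Keep the investigator's expectedness and attribution as fields on the form, and use them only to decide expedited reports.
4. In the Safety part of the statistical section and in the DSMB section, tabulate these events by arm, as patients with an event and number of events.

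If the sponsor already intends to collect every Grade 4 event, one sentence saying so settles that part.

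The cost is more AE forms for about 30 inpatients. They are already assessed daily for adverse experiences, so no extra tests are needed.

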- 3) To assess the effect of treprostinil inhalation on oxygenation in patients with acute hypoxic respiratory failure with, or at risk for, development of ARDS
- 4) To assess the effect of treprostinil inhalation on various biomarkers thought to be related to the pathogenesis and/or clinical course of ARDS.

We propose a proof of concept, double blinded, placebo controlled study of inhaled treprostinil for patients with "at-risk" or early ARDS. Early, or pre-ARDS will be defined as acute hypoxemia and unilateral pulmonary infiltrates in patients presenting with conditions that are conducive to ARDS (e.g. pneumonia, sepsis, aspiration, trauma) but do not yet meet criteria for ARDS: require mechanical ventilation, bilateral infiltrates on CXR, and PaO_2/FiO_2 ratio < 300. The primary outcome will be PaO_2/FiO_2 ratio. We will also measure other physiologic and clinical outcomes and levels of inflammatory and pro-fibrotic biomarkers. This exploratory initial study will enroll 30 patients to assess feasibility and safety in this population.

Hypothesis:

- 1. Treprostinil inhalation is safe at planned dose titration in patients with acute hypoxemic respiratory failure
- 2. Treprostinil will improve oxygenation and other secondary outcomes related to mechanical ventilation initiation and duration, as well as exhibit effects on ARDS-related pro-inflammatory and pro-fibrotic biomarkers.

Study Design:

- 1) Single Center, proof of concept, 2:1 active drug to placebo controlled, double-blinded
- 2) Target of 30 patients enrolled
- 3) Patients will be randomized to receive either treprostinil or saline inhalation placebo
- 4) Patients will be followed to hospital discharge or day 28, whichever comes first. Those discharged prior to day 28 will be assumed free of mechanical ventilation and alive unless readmitted in that period. This will be confirmed by phone.

Sample Size/Interim Monitoring:

1) This is primarily a feasibility, safety and proof of concept trial.

Version: 02-09-2018

- 2) The primary endpoint is Change in PaO₂/FiO₂ ratio from Study Day 0 to 2, 7
- 3) Trial progress will be monitored by an independent Data and Safety Monitoring Board to determine if the study should stop for safety reasons. The first interim review will occur6 months following enrollment of the first patient or after the first 15 patients (which-ever occurs first) have been enrolled.

Inclusion Criteria:

- 1) Adults age 18-80 years.

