Sample size calculations are based on simple t tests. Assuming a change in PaO_2/FiO_2 ratio of 15 in the intervention group and 10 in controls, a standard deviation of 6 (effect size of 0.833), and power of 0.80, the study would require 34 patients in the intervention group and 17 patients in the control group for a 2-sided test with significance level p < 0.05. While we will not approach these numbers, they serve to provide a framework as to the sample size needed to observe clinically meaningful changes in oxygenation as statistically significant. This current proposal centers on safety and feasibility, and thus does not meet the statistical criteria needed to observe minimally significant changes in oxygenation. The planned sample size of 30 total participants has 80% power to produce a 2-sided 80% confidence interval with lower confidence limit above 0 if the true effect size is 0.833.

Twenty-eight day ventilator-free days is a continuous variable. The mean 28 day ventilator free

Version: 02-09-2018

days for the control group of the most recent ARDS network trial was 15 days (95% CI 14.1 – 15.9). The patients enrolled for this trial will have significantly more ventilator free days as a number of them will not require mechanical ventilation at all. A study with 100 patients would have a power of 0.8 to show a 3 day difference in 28 day ventilator free days assuming a value of 22 for controls and 25 for intervention patients, with a SD of 5 days. Since this is an initial, smaller feasibility and proof of concept trial, we will not be able to obtain this level of statistical rigor.

Study feasibility will be assessed by enrollment rate over the first 6 months of the study. If the enrollment rate at that time suggests high feasibility such that the enrollment target of 30 patients can be exceeded easily within the funded enrollment period, we will consider amending the protocol to enroll a small number of additional subjects. This will be discussed and reviewed by the study DSMB. [name], Department of Biostatistics, UNC will provide statistical support.

Part 3. Data Collection and Site Monitoring

Data Collection

Research coordinators will collect data and enter it directly into a computer-based data entry system managed by the TRACS institute or on paper data forms.

Site Monitoring

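### The three numerical conditions for suspending enrolment start only after 30 patients, which is the whole planned sample, so as written they can suspend none of the planned enrolment

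*Combined protocol and SAP*

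**What the plan says.** Study Stopping Rules introduces its list with "The principle conditions for suspension of study enrollment and review of safety by the DSMB will be", followed by the timing line "After enrollment of the first 30 patients". Three conditions come under that line:

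- an imbalance above 4 to 1 in Grade 4 adverse events;
- an imbalance above 4 to 1 in patients intubated and ventilated;
- 28-day mortality above 60% in either arm.

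The same section says that a statistical "stopping rule based on mortality or even Grade IV Adverse events is not possible" at this size. It adds that a clinical rule based on Grade 4 events or intubation "has served as the stopping rule for this study to date".

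On sample size, Study Design gives "Target of 30 patients enrolled", and Sample size calculation says "The planned sample size of 30 total participants has 80% power" for its confidence-interval criterion. On going further, the latter says only that, if enrolment is quick, "we will consider amending the protocol to enroll a small number of additional subjects".

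On monitoring, Sample Size/Interim Monitoring states: "Trial progress will be monitored by an independent Data and Safety Monitoring Board to determine if the study should stop for safety reasons". The Safety analysis and DSMB sections schedule reviews every 6 months or after 15 patients, whichever comes first, and the Safety analysis section makes them unblinded.

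**The concern.** A condition for suspending enrolment can work only while there are patients left to enrol. Here the start of the conditions coincides with the end of the planned enrolment.

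Safety is the trial's first hypothesis. During the planned 30 patients, enrolment can be paused by DSMB judgement or by a clinical rule with no printed threshold, but not by the conditions the protocol calls its principal ones.

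Four points inside the conditions also leave the DSMB to guess:

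- **Direction.** The Grade 4 trigger names none. The intubation trigger speaks of an imbalance favouring the intervention, which can mean more or fewer intubations on treprostinil.
- **Unit.** The intubation trigger counts patients. The Grade 4 trigger could count events or patients.
- **Zero placebo events.** A ratio above 4 to 1 is undefined when the placebo count is zero.
- **Mortality reference.** The 60% limit is set against about 45% mortality for ARDS in general ICU populations, while the section describes patients not yet ventilated.

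**Working it through.** **1. Confirm that 30 is the full planned sample.** Inputs from Sample size calculation: difference 15 − 10 = 5, SD 6, so d = 5/6 = 0.833; 2:1 allocation gives 20 and 10; two-sided 80% interval.

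Noncentrality = 0.833 / √(1/20 + 1/10) = 2.15 on 28 degrees of freedom. Power by noncentral t is 0.799, which reproduces the stated 80%. The power statement therefore uses 30 as the total.

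**2. Timing.** Planned enrolment left when the conditions begin: 30 − 30 = 0.

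**3. Zero placebo events.** The plan states no operating characteristics for the ratio triggers, so the event rates below are assumptions. Let X be treprostinil patients with an event (of 20) and Y placebo patients with an event (of 10), with excess on treprostinil as the trigger direction. If Y ≥ 1, the rule fires when X > 4Y. If Y = 0, suppose it fires when X ≥ k:

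P(fires) = Σ over y ≥ 1 of P(Y = y)·P(X > 4y) + P(Y = 0)·P(X ≥ k)

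At 10% in both arms the first term is 0.0167 and P(Y = 0) = 0.9^10 = 0.3487. With k = 1, P(X ≥ 1) = 1 − 0.9^20 = 0.8784, so P(fires) = 0.0167 + 0.3487 × 0.8784 = 0.323. The other cells follow in the same way (single look at 20:10, equal rates):

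| True rate, both arms | Any active event v 0 fires | At least 3 v 0 | At least 5 v 0 | Zero placebo never fires |
|---|---|---|---|---|
| 10% | 0.323 | 0.129 | 0.032 | 0.017 |
| 20% | 0.209 | 0.188 | 0.142 | 0.102 |
| 30% | 0.147 | 0.146 | 0.141 | 0.119 |

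The convention matters most at low rates and little by 30%.

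**4. Which rates are plausible for intubation?** Sample size calculation assumes 22 ventilator-free days in controls, a mean loss of 28 − 22 = 6 days. No patient can lose more than 28, so at least 6/28 = 21% of controls are ventilated or dead. At that rate P(Y = 0) = (22/28)^5 = 0.30 with 5 placebo patients and (22/28)^10 = 0.09 with 10. Some of those losses could be deaths without intubation. The plan gives no rate for Grade 4 events.

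**5. Repeated looks.** Take looks at 15 patients (10:5) and 30 patients (20:10), with at least 3 v 0 needed, by exact enumeration:

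- equal 10% rates: 0.042 at the first look + 0.100 at the second only = 0.14, against 0.13 for one look at 30;
- equal 20% rates: 0.119 + 0.115 = 0.23, against 0.19.

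**6. Mortality limit.** Above 60% means at least 13 of 20 or at least 7 of 10 deaths. With the same true mortality in both arms, P(either arm) = 1 − (1 − a)(1 − b), where a and b are the two binomial tails.

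- At 45%: 1 − (1 − 0.058)(1 − 0.102) = 0.154.
- At 30%: 1 − (1 − 0.0013)(1 − 0.0106) = 0.012.
- At 20%: 0.001.

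The 30% and 20% rates are assumptions, since the documents give no rate for the enrolled population.

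**The case against.** **The first 30 patients are supervised.** This stands. A reader might infer from the timing line that nothing protects them, and the documents do not support that. There are unblinded DSMB reviews with authority to stop, individual withdrawal criteria, expedited reporting, and the clinical rule in use. What remains is that no threshold or timing is printed for that rule.

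**The conditions still do something.** This also stands. The section couples suspension with DSMB review. After patient 30, the conditions could prompt a review while late patients are on drug or in their 28-day follow-up. The phrase about the first 30 also fits an extension. But an extension is only to be considered, and prompting a late review does not suspend planned enrolment.

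**The zero-event gap may be rarer than it looks.** A reader might infer that a zero placebo count is the usual outcome. That depends on assuming a low rate: at 5%, its probability is 0.77 with 5 placebo patients and 0.60 with 10. The plan's own ventilator-free-day assumption gives about 0.30 and 0.09 for ventilation or death. The gap is real, but how often it matters depends on the event.

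**No statistical rule is feasible at this size.** The protocol says so, and nothing here asks for one.

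**The DSMB charter may settle the details.** It may. It is cited but is not among the documents, so the four wording points are requests to clarify.

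**Conclusion.** The timing is wrong as written. Read with the planned sample of 30, the three numerical conditions can suspend 0 of 30 planned enrolments. This rests only on the protocol's text and is held with high confidence. It does not mean that the trial lacks safety monitoring or that the conditions are wholly without effect.

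The four clarifications are secondary and depend on what the charter says. The zero-event convention moves the single-look chance of firing between 0.017 and 0.32 at equal 10% rates, but only between 0.10 and 0.21 at equal 20%. These figures assume patient counts, the stated 20:10 split and one look, so they do not describe a rule checked repeatedly. Firing means suspension and DSMB review, not termination.

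**What to change.** Reconcile Study Stopping Rules with Study Design, Sample Size/Interim Monitoring, the Safety analysis section, Sample size calculation and the DSMB section. Replace the timing line with wording such as: during the planned enrolment and any extension, evaluated at each scheduled DSMB review. State whether the clinical rule used so far is the same as these conditions; if not, print its threshold and timing.

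In the same edit, unless the charter already does so, the sponsor and DSMB should state:

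- the direction of the Grade 4 and intubation triggers;
- whether the Grade 4 ratio counts events or patients;
- the rule when there are no placebo events;
- why a limit above 60%, referenced to about 45% in general-ICU ARDS, suits patients not yet ventilated.

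No threshold is proposed here.

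The cost is protocol wording and matching charter text, since the reviews already exist. The downside is that some pauses will be false alarms, and repeated looks raise that chance above the single-look figures. Any convention should therefore be assessed under the actual review schedule before it is adopted.
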